6.4 Secondary Endpoints

- Incidence of administration site reactions
- Biochemical safety and tolerability (hematology, serum chemistry, coagulation, CH50)
- Geometric mean titers of anti-HAAH antibodies by dose
- Antigen-specific Cytotoxic CD8+ T-lymphocytes (CTL) responses by dose
- Production of B cell and T cell response of interest

Clinical Secondary Endpoints:

- Change in the prostate-specific antigen (PSA) velocity
- Reduction in the PSA doubling time from pre-baseline

Pharmacodynamic Secondary Endpoints:

- Duration of antigen-specific anti-HAAH antibody titers
- Changes in the amplitude or duration of the production of anti-HAAH antibodies
- Correlation of anti-HAAH titers and serum HAAH levels

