7.4.5 Derived Variables

- Non Treatment Emergent Adverse Events include all AEs that stopped the day prior to the first vaccination, started prior to the first vaccination but did not increase in severity or relationship during treatment, or started more than 30 days after *the final study treatment administration* date.
- Treatment Emergent Adverse Events (TEAEs) include all AEs that start on or after the first study treatment administration, or AEs that are present prior to the first administration, but their severity or relationship increases after the first administration up to and including 30 days after the final administration date.
- Change from baseline will be calculated as the observed value at the current visit or time point minus the observed value at baseline.
- Number of doses administered will be calculated for each subject by summing the number of doses administered over all visits.
- *Prior medications* include all medications that have a start date prior to the date of first study treatment administration.
- Concomitant medications include all medications that are taken on or after the date of first study treatment administration.
- The end of treatment phase visit will be the visit immediately after the last visit where treatment was administered. This visit will be the first follow up visit for subjects who have any follow up visits, or the End of Study visit for all other subjects.

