7.4.10 Baseline Values

Baseline values are the values obtained prior to the first vaccination on Day 1. If the baseline value is missing, the value at Screening will be treated as the baseline.

8 Summary of Study Data

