8.5 Clinical Analysis

PSA will be summarized descriptively for each dosage group by visit for the observed value as well as for the change from baseline value (Day 1). Subjects will be summarized through Day 43 using the assigned dose level as the treatment group. For additional treatment visits, follow up visits, and end of study, subjects will be summarized by cohort and by the dose level the subject took at the visit immediately prior to the current visit—this allows for subjects who changed their dose level to be summarized at the new dose level.

PSA velocity (ng/mL/year) will be estimated by the slope of the least-square regression line fit to PSA versus time in years [1]. PSA velocity will be calculated using PSA values between Day 1 and Day 43, and subjects will be summarized using the assigned dose level as the treatment group. Also, to account for additional treatment visits, PSA velocity will be calculated using PSA values between Day 1 and the end of treatment phase visit, and subjects will be summarized by cohort and by the dose level the subject took at the last additional treatment visit. Finally, to account for follow up visits, PSA velocity will be calculated using PSA values between Day 1 and the end of study visit, and subjects will be summarized by cohort and by the dose level the subject took at the last treatment visit prior to the end of study.

PSA doubling time (months) will be estimated as follows for each visit range [1]:

- 1) Calculate the natural log-transform of all PSA observations [log(PSA)] in the visit range
- 2) Determine the slope of the least-square regression line of log(PSA) versus time in months of PSA measurement; convert the slope from years to months by multiplying the slope in years by the factor 12.
- 3) Divide the natural log of 2 [log(2)] by the slope calculated in step 2.

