PSA doubling time will be estimated for 3 visit ranges: 1) up to and including Day 1 (baseline); 2) Day 1 through Day 43; 3) Day 1 through end of treatment phase visit; and 4) Day 1 through end of study. The baseline value will use all PSA values collected in the Medical History eCRF as well as any screening or Day 1 values in the safety laboratory data extract. For each post-baseline date range, each subject's PSA doubling time will be compared to their baseline value, and the number of subjects who have improved in the parameter (longer or negative doubling time) will be summarized, as well as the number of subjects who have not improved or who are worse (no change or shorter doubling time). For the summary from Day 1 through Day 43, subjects will be summarized using the assigned dose level as the treatment group. For Day 1 through end of treatment phase visit, subjects will be summarized by cohort and by the dose level the subject took at the last additional treatment visit and for Day 1 through end of study, subjects will be summarized by cohort and by the dose level the subject took at the last additional treatment visit and for Day 1 through end of study, subjects will be summarized by cohort and by the dose level the subject took at the last additional treatment visit and for Day 1 through end of study.

All PSA analyses will be conducted on the Safety Population.

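### SAP 8.5 summarises PSA velocity only in windows that start at Day 1, so the listed endpoint, a change in PSA velocity, has no defined baseline and no contrast

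*SAP*

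**What the plan says.** SAP 6.4 lists the endpoint as "Change in the prostate-specific antigen (PSA) velocity", and Protocol 4.2.3 uses the same words. Neither says change from what.

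SAP 8.5 estimates velocity by least-squares regression of PSA on time, in ng/mL/year, over three windows:
- The first: "PSA velocity will be calculated using PSA values between Day 1 and Day 43".
- The second runs from Day 1 to the end of treatment phase visit. SAP 7.4.5 defines that visit as the one immediately after the last treatment: "This visit will be the first follow up visit for subjects who have any follow up visits".
- The third: "PSA velocity will be calculated using PSA values between Day 1 and the end of study visit".

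For each window the section says how patients are grouped for the summary, and nothing more.

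Doubling time is handled differently in the same section. It has a range ending at Day 1, with named sources: "The baseline value will use all PSA values collected in the Medical History eCRF", plus screening and Day 1 laboratory values. It also has a within-patient contrast, in which each patient's "PSA doubling time will be compared to their baseline value" and patients are counted as improved or not improved.

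Two general rules might bear on velocity. Under SAP 7.4.5, change from baseline "will be calculated as the observed value at the current visit or time point minus the observed value at baseline". Under SAP 7.4.10, "Baseline values are the values obtained prior to the first vaccination on Day 1", with the Screening value used if that is missing.

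**The concern.** A change needs two velocities, and SAP 8.5 provides only post-Day-1 slopes. A programmer who follows it exactly produces three velocity summaries and no change, although SAP 7.4.1 states that the planned analyses agree with the protocol. At stake is whether one listed clinical secondary endpoint can be reported as specified. The MTD, the DLT evaluation and the sample size are untouched.

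**Working it through.** **1. Do the general rules fill the gap?** SAP 7.4.5 subtracts an observed baseline value from an observed value at a visit. SAP 7.4.10 makes that baseline the pre-vaccination Day 1 value. That works for PSA itself. A velocity is a slope and needs at least two dated PSA values, so these rules yield no baseline velocity. None of the three velocity windows is pre-treatment, whereas one of the four ranges listed for doubling time is.

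**2. Could the three windows be compared with one another?** Schedule (SAP Table 4-1, nine doses): doses at day offsets 0, 21, ..., 168 from Day 1, then six follow-up visits at 28-day steps, 196 to 336. PSA is scheduled at each. The windows hold 3, 10 (9 + 1) and 15 (9 + 6) values. They are nested and share the first three values.

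Assumed patient, no noise: PSA(t) = 4 × 2^(t/DT), with DT = 6 months and a month of 30.4375 days. Velocity b = Σ(t − t̄)(y − ȳ)/Σ(t − t̄)², with t in years of 365.25 days.

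First window: PSA is 4.000, 4.332 and 4.691. With equal spacing, b = (4.691 − 4.000)/(42/365.25) = 0.691/0.115 = 6.01. The same formula gives the rest:

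| Window | Values | Velocity (ng/mL/year) | Relative to first | log(PSA) slope per year |
|---|---|---|---|---|
| Day 1 to Day 43 | 3 | 6.01 | – | 1.386 |
| Day 1 to end of treatment phase | 10 | 8.14 | +35% | 1.386 |
| Day 1 to end of study | 15 | 10.92 | +82% | 1.386 |

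Velocity climbs while the growth rate is constant, so differences between windows do not measure a change in the disease course.

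**3. How would a post-minus-baseline change behave?** Assume six equally spaced values over the 12 months ending at Day 1. For the same patient the baseline velocity is 2.96, so the changes are 6.01 − 2.96 = +3.06 (from unrounded slopes), +5.19 and +7.96, again with an unchanged doubling time.

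The contrast can even hide a slowing. Assume PSA 2.0 at Day 1, five roughly quarterly earlier values, and a doubling time of 6 months before Day 1 and 12 months after. Baseline velocity is 1.48 and the post-baseline velocities are 1.44, 1.67 and 1.92, so the changes are −0.04, +0.19 and +0.44.

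**4. Precision of one patient's change.** Assume independent residuals with SD σ and six pre-values over 12 months; the Day 1 value enters both slopes. Then Var = σ²[1/S_post + 1/S_pre − 2·w_post·w_pre], where S = Σ(t − t̄)² and w = (t_Day1 − t̄)/S.

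For Day 1 to 43, S_post = 0.00661, S_pre = 0.700 and w_post·w_pre = −6.21. The bracket is 151.26 + 1.43 + 12.42 = 165.11, with square root 12.85.

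| Window | SE at σ = 0.1 | SE at σ = 0.5 | Change at DT 6 months | Change at DT 36 months |
|---|---|---|---|---|
| Day 1 to Day 43 | 1.28 | 6.42 | +3.06 | +0.11 |
| To end of treatment phase | 0.25 | 1.25 | +5.19 | +0.16 |
| To end of study | 0.17 | 0.83 | +7.96 | +0.20 |

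(DT 36 months: baseline velocity 0.825; post-baseline 0.937, 0.983 and 1.028.)

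**5. The third window.** The 15 values assume that end of study follows six 28-day visits, as Table 4-1 suggests. The study-duration text in the Protocol synopsis and in SAP section 4 places an end of study visit 28 days after the last dose. On that reading the third window would hold 10 values and coincide with the second. These passages need to be reconciled.

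**The case against.** The strongest reply is that the SAP is not the whole specification. SAP 10.2 refers to separate shells and programming notes, which were not available and could contain the derivation. This stands as a limit. A reader might infer that the contrast would be chosen after the data are seen; the documents do not establish that. What they show is that the SAP text leaves it undefined.

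A reader might also point to the velocity table and listing titles, none of which names a change. That is not evidence. The same titles are silent about the doubling-time comparison, which SAP 8.5 does plan.

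Nor do the documents require a pre-treatment reference. The doubling-time endpoint is worded as relative to pre-baseline and the velocity endpoint is not, so using values up to Day 1 is a choice, made here to match doubling time.

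Finally, doubling time is the better-scaled measure and is already compared with baseline, and a linear velocity change misleads under exponential growth. Both points stand and lower the weight of this one. They do not remove it: velocity is a separate listed endpoint, and the doubling-time plan counts improved patients rather than sizing a velocity change.

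**Conclusion.** The point holds on the text: SAP 8.5 together with SAP 7.4.5 and 7.4.10 gives summaries of velocity and does not give the listed change. This rests on no numerical assumption. The impact is minor: a descriptive endpoint in about 18 patients, with no part in the MTD and partly covered by doubling time.

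The figures illustrate two things only: the planned windows cannot stand in for the contrast, and the contrast needs a caveat. They depend on the assumed PSA level, doubling time, pre-study sampling and residual SD.

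A reader might infer from the smaller standard errors that the two longer windows give a dependable per-patient change. That is not supported. At a 36-month doubling time the end-of-treatment change of 0.16 is below its SE throughout the assumed range (0.25 to 1.25), and the end-of-study change of 0.20 is set against 0.17 to 0.83.

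**What to change.** Amend SAP 8.5 only:
1. Calculate a baseline PSA velocity from PSA values up to and including Day 1, using the sources already named for baseline doubling time. State that the reference period is chosen to match doubling time.
2. For each of the three post-baseline windows, summarise the per-patient change, post minus baseline.
3. State that linear velocity rises under an unchanged doubling time, so the change is to be read beside the planned doubling-time comparison. Showing the log(PSA) slope as well is optional.

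When making the edit, settle which visit ends the third window.

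The cost is SAP wording and derived variables from PSA data already in use, with no protocol amendment and no new data collection. Downsides: patients with too few pre-study PSA values have no change score. The change leans toward apparent worsening. It is imprecise for Day 1 to 43 and, with long doubling times, can be so in the longer windows too. SAP 8.5 sets no earliest date for the Medical History PSA values, so baseline velocity inherits that open point from baseline doubling time.

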5.2.3 Removal of Patients from Treatment or Assessment

The patients may withdraw from treatment with study product if they decide to do so, at any time and irrespective of the reason, or this may be the Investigator's decision to protect the safety of the patient. All efforts should be made to document the reason for discontinuation and this should be documented in the electronic case report form (eCRF).

Other criteria for possible discontinuation are:

- PSADT < 90 days
- Unacceptable toxicity as judged by the Principal Investigator

Adverse events which are dose-limiting toxicities

Patient is lost to follow-up

Patients will be followed up according to the study procedures as specified in this protocol up to the scheduled date of study completion, or up to recovery or stabilization of a followed-up AE, or the initiation of post study treatment, whichever comes last.

If possible, and after the permanent discontinuation of treatment, the patients will be assessed using the procedure normally planned for the 'end of study'.

The patients may withdraw from the study follow-up schedule, before study completion if they decide to do so, at any time and irrespective of the reason, or this may be the Investigator's decision:

Patients who are lost to follow-up:

- The Investigator should make every effort to re-contact the patient, to identify the reason why he/she failed to attend the visit, and to determine his/her health status, including at least his/her vital status. Attempts to contact such patients must be documented in the patient's records (e.g. times and dates of attempted telephone contact, receipt for sending a registered letter).
- Patients who did not complete the study and for whom no endpoint data are available will be considered as lost to follow-up.

The statistical analysis plan will specify how these patients lost to follow-up for their primary endpoints will be considered.

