5.4.1.2 Prohibited Medications or Treatments During Study

Medications such as those listed below are not permitted in the course of the trial:

- Concurrent treatment with other investigational drugs
- Concurrent treatment with any other anticancer therapy including radiotherapy

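### SAP 8.5 fits end-of-study PSA doubling time and velocity to all PSA values with no cut at the start of another anticancer therapy, so a patient who failed on SNS-301 can be tabulated as improved

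*SAP*

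**What the plan says.** SAP 8.5 sets the end-of-study velocity window: "PSA velocity will be calculated using PSA values between Day 1 and the end of study visit". For doubling time, step 1 is "Calculate the natural log-transform of all PSA observations [log(PSA)] in the visit range" and step 3 is "Divide the natural log of 2 [log(2)] by the slope calculated in step 2". The last two of its ranges are "3) Day 1 through end of treatment phase visit; and 4) Day 1 through end of study". For each post-baseline range, "the number of subjects who have improved in the parameter (longer or negative doubling time) will be summarized". This count exists for doubling time only; velocity is summarised without it. All PSA analyses use the Safety Population.

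SAP 7.4 keeps follow-up assessments out of tables unless the plan notes otherwise. Section 8.5 does so, and Table 14.2.3.2.3 is planned for the end-of-study range.

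Two protocol passages bear on other therapy. Section 5.4.1.2 lists as not permitted in the course of the trial: "Concurrent treatment with any other anticancer therapy including radiotherapy". Section 5.2.3 gives three markers for the end of follow-up: the scheduled completion date, resolution of a followed adverse event, "or the initiation of post study treatment, whichever comes last". After SNS-301 stops, PSA is drawn monthly for 6 months (Protocol 5.1).

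Neither document says how PSA values drawn after another anticancer therapy starts are to be analysed.

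**The concern.** A PSA value drawn after another anticancer therapy begins reflects that therapy as well as SNS-301. SAP 8.5 puts it into the same straight-line fit as the on-treatment values. If the later therapy lowers PSA, the fitted slope flattens or turns negative, and the patient moves towards the improved row.

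The direction favours SNS-301. Exclusion criterion 1 removes patients with a baseline doubling time under 3 months, and treatment stops when doubling falls below 90 days. A patient stopped for that reason would normally be classed as not improved on the data up to the stop. The end-of-study fit can reverse that label. Change in velocity and in doubling time are the two clinical secondary endpoints, and clinical activity is a secondary objective in SAP 3, so the count is likely to be read as a signal of activity even though it is descriptive.

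**Working it through.** The plan gives no figure to reproduce here, so the check applies the SAP 8.5 rules to an assumed patient.

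**From the documents.** Dosing every 21 days, at most 9 doses; follow-up every 28 days for 6 months (six visits); doubling time = ln 2 / least-squares slope of ln(PSA) on months; velocity = least-squares slope of PSA on years.

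**Assumed.** Day 1 PSA 5 ng/mL (affects velocity only); on-treatment doubling time 85 days; 6 doses; other therapy on Day 150; PSA then falls by 50%, 80% or 90% of its Day 150 value with a 30-day time constant; no measurement noise.

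**Step 1, PSA path.** Up to Day 150, PSA = 5 × 2^((day − 1)/85), which reaches 5 × 2^(149/85) = 16.85 ng/mL. After that, PSA = 16.85 × [(1 − f) + f × exp(−(day − 150)/30)], where f is the fall. With f = 0.8:

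| Day | 1 | 22 | 43 | 64 | 85 | 106 | 134 | 162 | 190 | 218 | 246 | 274 |
|---|---|---|---|---|---|---|---|---|---|---|---|---|
| PSA | 5.00 | 5.93 | 7.04 | 8.36 | 9.92 | 11.77 | 14.79 | 12.41 | 6.92 | 4.77 | 3.92 | 3.59 |

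**Step 2, fits.** With ln 2 = 0.693 and 30.44 days per month:

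| Data used | Slope of ln(PSA) per month | Doubling time (months) | Velocity (ng/mL/year) |
|---|---|---|---|
| Cut at Day 150 | 0.248 | 0.693/0.248 = 2.8 | +26.5 |
| All, 50% fall | 0.0529 | 13.1 | +4.8 |
| All, 80% fall | −0.0530 | −13.1 | −3.3 |
| All, 90% fall | −0.121 | −5.7 | −6.0 |

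The stopping threshold of 90 days is 90/30.44 = 2.96 months, so the cut result is a failure. Each all-data result counts as improved against a baseline of up to 12 months. The end-of-treatment range, which ends at the first follow-up visit (Day 134), also gives 2.8 months.

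**Step 3, a case that moves less.** With 9 doses (last on Day 169), the same 85-day doubling and therapy on Day 281, the all-data slopes are 0.197, 0.168 and 0.154. Doubling times are 3.5, 4.1 and 4.5 months for the three falls. That is improved against a 3-month baseline but not against a 6-month one.

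**Step 4, a wider grid.** The grid has 80 assumed scenarios: 3, 4, 5, 7 or 9 doses; doubling time 2.0 or 2.9 months; falls of 30%, 50%, 80% or 95% with a 14-day half-life; therapy 28 or 84 days after the last dose. The end-of-study fit gives improved in 77, 59 and 47 of 80 at baselines of 3, 6 and 12 months. The cut data and the end-of-treatment range give 0. These counts show sensitivity to assumptions; they are not probabilities.

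**Step 5, limit of the end-of-treatment range.** With 5 doses, 2.5-month doubling, an 80% fall and therapy 7 days after the last dose, that range gives 8.15 months, which is improved against a 6-month baseline.

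**Step 6, weight of one patient.** SAP 8.5 tabulates by cohort and dose level, with 3 or 6 patients per cohort: 1/3 = 33 and 1/6 = 17 percentage points.

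Time is taken in months throughout. The factor-of-12 conversion in SAP step 2 is a separate matter; it changes neither the sign nor the ranking against a baseline scaled the same way.

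**The case against.** The strongest reply is that the situation should rarely arise. Protocol 5.4.1.2 prohibits other anticancer therapy in the course of the trial, and the stated study duration includes the 6-month follow-up. An affected patient would be a protocol deviation. This stands as a limit on frequency. It does not settle the analysis: SAP 8.3 only lists deviations, and SAP 5 defines no per-protocol set, so the values stay in the fit.

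A reader might infer from Protocol 5.2.3 that the sponsor expects patients to start other treatment during follow-up. The text does not support that. It names the start of post-study treatment as one of three markers, gives no rate, and is ambiguous. Taken literally, though, it does not end follow-up when such treatment begins. The path the protocol describes for progression in follow-up is resuming SNS-301, not switching.

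The failure would also not be hidden. The end-of-treatment table, reasons for discontinuation, concomitant medications and full listings are all planned. This stands, and it lowers the severity. It does not correct the end-of-study count.

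Finally, the trial is single-arm Phase I with no formal analysis, and fitting all follow-up PSA is a recognisable choice. That is fair, but the plan should then state it and show what it does to the count.

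**Conclusion.** The point holds as a gap in the analysis rule. SAP 8.5 can label a patient who failed on SNS-301 as improved in Table 14.2.3.2.3, and it shifts velocity in the same direction. In the illustration, doubling time moves from 2.8 months to 13.1, -13.1 or -5.7 months. This rests on the assumed doubling time, timing and depth of PSA fall.

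Three stronger readings are not supported. The reversal is not automatic: in the 80-scenario grid, 3 do not flip at a 3-month baseline and 33 do not at 12 months. The expected number of affected patients cannot be derived from the documents. The end-of-treatment results (Table 14.2.3.2.2) are not generally compromised; they are affected only if other therapy starts before the first follow-up visit.

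This should be fixed before analysis. It concerns a descriptive secondary endpoint, and MTD and RP2D do not depend on it.

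**What to change.** In SAP 8.5, for the end-of-treatment and end-of-study ranges, use only PSA values drawn before the start date of any other anticancer therapy. Then:

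- Classify each patient as improved or not on the cut data. Do not bar patients who started other therapy from the improved row, since that would override a valid earlier result.
- Show the number who started other therapy beside the count, by cohort and dose level.
- Flag later PSA values in the listings.
- Keep the all-data fit as a sensitivity analysis.

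Start dates should already be available: Protocol 5.4.1 requires all treatments to be recorded, Table 1 collects concomitant medications at follow-up, and SAP 8.4 uses their start dates. Confirm that radiotherapy is captured with a date. Partial dates need a check, because SAP 7.4.8 can impute the first dose date when the month is unknown, and that would remove all post-baseline values.

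State separately how PSA values after resumption of SNS-301 are handled, since this cut does not touch them.

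The SAP change is a few sentences and one programming filter; the cost is fewer PSA points for affected patients. Protocol 5.2.3 and 5.4.1.2 should also be reconciled on whether follow-up continues once other treatment begins. That needs a protocol amendment; the SAP change does not have to wait for it.

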10.1 List of Tables, Figures, and Listings

Table No.	Description of Table	Population
4.1.1	Subject Disposition	All Subjects
4.1.2.1	Demographics and Baseline Characteristics	Safety
14.1.2.2	Demographics and Baseline Characteristics	Immunologic
14.2.1.1	Study Treatment Administration Through Day 43	Safety
14.2.1.2	Study Treatment Administration by Additional Treatment Visit	Safety
14.2.2.1	Concomitant Medications Through Day 43	Safety
14.2.2.2	Concomitant Medications For Additional Treatment Visits	Safety
14.2.3.1.1	Change from Baseline in PSA by Visit Through Day 43	Safety
4.2.3.1.2	Change from Baseline in PSA by Additional Treatment Visit	Safety
14.2.3.2.1	Summary of PSA Velocity and PSA Doubling Time Through Day 43	Safety
14.2.3.2.2	Summary of PSA Velocity and PSA Doubling Time Through End of Treatment	Safety
14.2.3.2.3	Summary of PSA Velocity and PSA Doubling Time Through End of Study	Safety
14.3.1.1.1	Summary of Worst Administration Site Reactions Through Day 43 by Grade	Safety
14.3.1.1.2	Summary of Worst Administration Site Reactions For Additional Treatment Visits by Grade	Safety
14.3.1.2.1	Summary of Administration Site Reactions by Visit Through Day 43 and Grade	Safety
14.3.1.2.2	Summary of Administration Site Reactions by Additional Treatment Visit and Grade	Safety
14.3.2.1.1	Overall Summary of Adverse Events Through Day 43	Safety
14.3.2.1.2	Overall Summary of Adverse Events For Additional Treatment Visits	Safety
14.3.2.2.1	Treatment-Emergent Adverse Events (TEAE) by System Organ Class and Preferred Term Through Day 43	Safety
14.3.2.2.2	Treatment-Emergent Adverse Events (TEAE) by System Organ Class and Preferred Term For Additional Treatment Visits	Safety
14.3.2.3.1	Treatment-Emergent Adverse Events (TEAE) by System Organ Class and Severity Through Day 43	Safety
14.3.2.3.2	Treatment-Emergent Adverse Events (TEAE) by System Organ Class and Severity For Additional Treatment Visits	Safety
14.3.2.4.1	Treatment-Emergent Adverse Events (TEAE) by Preferred Term and Relationship to Study Treatment Through Day 43	Safety
4.3.2.4.2	Treatment-Emergent Adverse Events (TEAE) by Preferred Term and Relationship to Study Treatment For Additional Treatment Visits	Safety
4.3.2.5.1	Serious Treatment-Emergent Adverse Events (TEAE) by System Organ Class and Preferred Term Through Day 43	Safety
4.3.2.5.2	Serious Treatment-Emergent Adverse Events (TEAE) by System Organ Class and Preferred Term For Additional Treatment Visits	Safety

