14.4.2.3	Mean (SD) of HAAH-Specific B Cells by Treatment	Immmunologic
14.4.3.1	Mean (SD) of B Cells by Treatment	Immmunologic
14.4.3.2	Mean (SD) of T Cells by Treatment	Immmunologic
14.4.3.3	Mean (SD) of CD4+ T Cells by Treatment	Immmunologic
14.4.3.4	Mean (SD) of CD8+ T Cells by Treatment	Immmunologic
14.4.3.5	Mean (SD) of CD3+, CD56+ Cells by Treatment	Immmunologic
14.4.3.6	Mean (SD) of NK Cells by Treatment	Immmunologic
14.4.3.7	Mean (SD) of Neutrophils by Treatment	Immmunologic
14.4.3.8	Mean (SD) of Eosinophils by Treatment	Immmunologic

9	Mean (SD) of Monocytes by Treatment Immmunol
Listing No.	Description of Listing
16.2.1.1	Subject Disposition
16.2.1.2	End of Treatment
16.2.1.2	Treatment Assignment and Analysis Populations
16.2.1.3	Elgibility
16.2.2.1	Protocol Deviations
16.2.2.2	Demographics
16.2.2.3	Oncology History
16.2.2.4	General Medical History
16.2.2.5	Tumor Burden Evaluation
16.2.3	Study Treatment Administration
16.2.4	Prior and Concomitant Medications
16.2.5	Immunological Results
16.2.6	Physician Administration Site Assessment
16.2.7	Adverse Events
16.2.8.1	Laboratory Results – Hematology and Coagulation
16.2.8.2	Laboratory Results – Chemistry and PSA
16.2.8.3	Laboratory Results – CH50
16.2.8.4.1	PSA Velocity and PSA Doubling Time Through Day 43
16.2.8.4.2	PSA Velocity and PSA Doubling Time Through End of Study
16.2.9	ECOG Performance Score
16.2.10.1	ECG Parameters
16.2.10.2 16.2.11	ECG Overall Interpretation Vital Signs
16.2.12	Physical Examination

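### SAP 8.5 step 2 mixes a monthly and a yearly time axis and inverts the conversion, so PSA doubling time comes out 12-fold or 144-fold too short if the conversion is applied

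*SAP*

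**What the plan says.** SAP 8.5 (Clinical Analysis) gives the derivation in three numbered steps, introduced by "PSA doubling time (months) will be estimated as follows for each visit range [1"]. Step 1 takes natural logs of the PSA values in the visit range. Step 2 has two clauses:

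- The first clause sets up the regression and its time axis: "Determine the slope of the least-square regression line of log(PSA) versus time in months of PSA measurement".
- The second clause, in the same sentence, adds a change of units for the slope: "convert the slope from years to months by multiplying the slope in years by the factor 12".

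Step 3 reads: "Divide the natural log of 2 [log(2)] by the slope calculated in step 2".

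The preceding paragraph of the same section sets up PSA velocity on a different axis: it "will be estimated by the slope of the least-square regression line fit to PSA versus time in years".

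PSADT is one of two clinical secondary endpoints (protocol 4.2.3, SAP 6.4). It feeds Tables 14.2.3.2.1 to 14.2.3.2.3, for example "Summary of PSA Velocity and PSA Doubling Time Through End of Treatment", and Listings 16.2.8.4.1 and 16.2.8.4.2. Section 8.5 also plans counts of subjects who have "improved in the parameter (longer or negative doubling time") compared with their own baseline.

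**The concern.** Step 2 has two separate faults.

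1. **Inconsistent axes.** A regression on months yields a slope per month. There is then no yearly slope to convert, yet the second clause converts one.
2. **Inverted conversion.** A rate per year becomes a rate per month on division by 12. Multiplying by 12 is right for turning a doubling time in years into one in months, but the SAP applies the factor to the slope, before the division in step 3.

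Nothing else in the two documents settles the matter. The protocol names the endpoint without a formula, SAP 7.4.5 (Derived Variables) does not cover it, and the shells and programming notes are in a separate document (SAP 10.2). What was programmed therefore cannot be seen.

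The study is descriptive (protocol 6.1), so the displayed values are themselves the result. A 144-fold error would probably be noticed. A 12-fold error gives believable numbers and is easier to miss.

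**Working it through.** **Inputs.** Reporting unit: months. Response: natural log of PSA. Formula: PSADT = ln 2 / slope. Conversion stated: slope × 12. All are from SAP 8.5. The test PSADT values are chosen for illustration.

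**Units.** If PSA doubles every T months, then ln PSA = constant + (ln 2 / T) × t, with t in months.

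- Slope per month: b_m = ln 2 / T
- Slope per year: b_y = 12 × b_m

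Hence b_m = b_y / 12. The stated factor of 12 should be 1/12.

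**Worked case, T = 12 months.** b_m = 0.6931 / 12 = 0.05776 and b_y = 0.6931.

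- Months axis, no conversion: 0.6931 / 0.05776 = 12.0 months (correct)
- Years axis, slope divided by 12: 0.6931 / (0.6931 / 12) = 12.0 months (correct)
- Months axis, slope × 12: 0.6931 / (12 × 0.05776) = 1.0 month (12-fold too short; this is the PSADT in years, labelled months)
- Years axis, slope × 12: 0.6931 / (12 × 0.6931) = 0.083 month, about 2.5 days (144-fold too short)

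**Other values.**

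| True PSADT (months) | Monthly slope × 12 | Yearly slope × 12 |
|---|---|---|
| 3 | 0.25 | 0.021 |
| 6 | 0.5 | 0.042 |
| 12 | 1.0 | 0.083 |
| 24 | 2.0 | 0.167 |
| 36 | 3.0 | 0.25 |
| 48 | 4.0 | 0.333 |
| −24 (falling PSA) | −2.0 | −0.167 |

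Least-squares fits to noise-free series gave ratios of exactly 12 and 144 for every PSADT tried. They covered Day 1 to Day 43, nine doses plus the first follow-up visit, and six follow-up visits.

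**Against the protocol's 3-month mark.** A displayed value under 3 corresponds to a positive true PSADT below 3 × 12 = 36 months, or below 3 × 144 = 432 months.

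**Improved/not-improved counts.** Let P be the post-baseline PSADT, B the baseline PSADT and k > 0 a common divisor. Then P/k > B/k exactly when P > B, and P/k < 0 exactly when P < 0. The counts therefore do not change for k = 12 or 144.

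This needs the same factor at baseline and afterwards. In 20,000 simulated subjects (assumed baseline PSADT 8 months, on-study PSADT 10 months, log-scale SD 0.15), a common factor changed no classification. Multiplying only the post-baseline slope by 12 changed about 82%.

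**The case against.** The strongest reply is that the step cannot be executed literally to give a wrong answer. The conversion acts on a yearly slope, but the regression in the same step is on months, so no yearly slope exists. The 12-fold error needs a programmer to multiply the wrong quantity, and the 144-fold error needs one to ignore the stated axis. The reporting unit, the regression axis and step 3 agree with one another and give the right value. The stray clause may be a slip for a legitimate conversion of time, or of a doubling time, from years to months.

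The effect is also limited. This is a Phase I study of approximately 18 patients whose primary endpoints are MTD, RP2D and DLTs. The only PSADT summary that 8.5 spells out is the count, which is robust to a common factor. Numeric PSADT summaries follow only from the general rule in SAP 7.4 and the table titles. PSA results are listed, so PSADT can be recomputed.

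Most of this stands as a limit on consequences: the error is conditional, and no wrong value has been shown. It does not rescue the step. A programmer who works through step 2 in order, fitting on months and then applying the factor, gets the 12-fold error. One who carries over the yearly axis from the velocity paragraph gets the 144-fold error. The only way to the right answer is to disregard an explicit instruction or reverse it.

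**Conclusion.** The concern holds. Step 2 contradicts itself, and its conversion is in the wrong direction. This is certain from the text.

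The size depends on the conversion being applied: 12-fold too short on a monthly slope, 144-fold too short on a yearly slope, and no error if the clause is ignored. Which of these was programmed is unknown.

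The results at risk are the PSADT values in Listings 16.2.8.4.1 and 16.2.8.4.2, any PSADT values summarised in Tables 14.2.3.2.1 to 14.2.3.2.3, and any reading of them against absolute marks in months or days. PSA velocity is fitted on years with no conversion and is not affected. The improved/not-improved counts stand, provided one factor is used for every visit range. The documents do not show any eligibility, discontinuation or treatment-failure decision being made from this formula.

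Because this is the only prespecified derivation of a secondary endpoint, it must be corrected before any PSADT value is reported.

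**What to change.** Replace step 2 with: *Determine the slope of the least-squares regression of log(PSA) on time in months and use that slope without conversion; if time is held in years, divide the slope by 12.* Step 3 then stands: PSADT (months) = log(2) / slope per month. Naming a single axis and deleting the conversion clause altogether would be cleaner still.

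Before PSADT is reported, check the program on one case: a yearly slope of 0.6931 (0.05776 per month) must return 12.0 months. Confirm that the same code is used for the baseline and post-baseline ranges.

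The cost is one sentence in the SAP, one program check, and one line of code if the conversion was programmed as written. No data collection, sample size or clinical rule is touched.
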